2.2.1 Randomization and drug dispensing irregularities

Randomization and drug-dispensing irregularities occur whenever:

1. A randomization is not in accordance with the protocol-defined randomization method, such as a) an ineligible patient is randomized, b) a patient is randomized based on an incorrect stratum, c) a patient is randomized twice, or d) in a dynamic randomization scheme the treatment assignment is, in fact, not random, due to a computer program error.

OR

2. A patient is dispensed an IMP kit not allocated by the protocol-defined randomization, such as a) a patient at any time in the study is dispensed a different treatment kit than as randomized (which may or may not contain the correct-as-randomized IMP), or b) a nonrandomized patient is treated with IMP reserved for randomized patients.

Randomization and drug-dispensing irregularities will be monitored throughout the study and reviewed on an ongoing basis.

All randomization and drug-dispensing irregularities will be documented in the clinical study report. If the number of irregularities is large enough to make a tabular summary useful, the irregularities will be categorized and summarized among randomized patients (number and percentages). Nonrandomized but treated patients will be described separately. Listings with additional relevant details will be provided in appendices.

Randomization and drug-dispensing irregularities to be prospectively identified include but are not limited to:

Randomization and drug allocation irregularities

Kit dispensation without IRT transaction

Erroneous kit dispensation

Kit not available

Randomization by error

Patient randomized twice

Stratification error

Patient switched to another site

2.3 ANALYSIS POPULATIONS

Patients treated without being randomized will not be considered randomized and will not be included in any efficacy population.

The randomized population includes any patient who has been allocated to a randomized treatment regardless of whether the treatment kit was used.

For any patient randomized more than once, only the data associated with the first randomization will be used in any analysis population. The safety experience associated with any later randomization will be assessed separately.

The safety experience of patients treated and not randomized will be reported separately, and these patients will not be in the safety population.

2.3.1 Efficacy populations

Efficacy analyses will be based on the treatment group allocated by the IRT according to the randomization schedule at randomization visit (as randomized), irrespective of the treatment actually received.

2.3.1.1 Intent-to-treat population

Efficacy analyses will be based on the ITT population, defined as all randomized patients, irrespective of compliance with the study protocol and procedures. Patients will be analyzed for efficacy analyses according to the treatment group to which they are randomized.

2.3.1.2 Completers population

The completers population is a subset of the ITT population who complete the 52-week Treatment Period and do not start rescue therapy. Sensitivity and subgroup analyses for the primary endpoint of change from Baseline to Week 52 HbA1c comparisons will be conducted on this population.

2.3.2 Safety population

Safety analyses will be based on the safety population, defined as all randomized patients who receive at least one dose of double-blind IMP (regardless of the amount of treatment administered). Patients will be analyzed for safety analyses according to the treatment actually received.

In addition:

- Nonrandomized but treated patients will not be part of the safety population; however, their safety data will be presented separately.
- Randomized patients for whom it is unclear whether they took the IMP will be included in the safety population as randomized.
- For patient receiving both sotagliflozin and placebo during the trial, the treatment group allocation for as-treated analysis will be sotagliflozin group (depending on the treatment kits taken [400 mg or 200 mg]).
- For patients receiving both sotagliflozin 400 mg (treatment kits) and 200 mg (treatment kits) during the trial, the treatment group allocation for as-treated analysis will be sotagliflozin 200 mg group.
- For patients receiving both sotagliflozin and glimepiride during the trial, the treatment group allocation for as-treated analysis will be sotagliflozin group (depending on the treatment kits taken [400 mg or 200 mg]).
- For patients receiving both glimepiride and placebo during the trial, the treatment group allocation for as-treated analysis will be glimepiride group.
- Randomized patients will be excluded from the safety population only if there is documented evidence (ie, all study dates recorded as no medication taken) that patients have not taken the study medication. If a patient is dispensed double-blind IMP and is lost to follow-up without any documented evidence, the patient will be considered exposed.

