#### **11.3.3 Safety population**

Safety analyses will be based on the safety population, defined as all randomized patients who receive at least 1 dose of double-blind IMP (regardless of the amount of treatment administered).

Patients will be analyzed for safety analyses according to the treatment actually received.

In addition:

- Nonrandomized but treated patients will not be part of the safety population, but their safety data will be presented separately.
- Randomized patients for whom it is unclear whether they took the study medication will be included in the safety population as randomized.

- When a patient is exposed to both sotagliflozin and placebo, the patient will be analyzed in the sotagliflozin group (depending on the treatment kits taken [400 mg or 200 mg]).
- When a patient is exposed to both sotagliflozin 400 mg (treatment kits) and 200 mg (treatment kits), the patient will be analyzed in the sotagliflozin 200 mg group.
- When a patient is exposed to both sotagliflozin and glimepiride, the patient will be analyzed in the sotagliflozin group (depending on the treatment kits taken [400 mg or 200 mg]).
- When a patient is exposed to both glimepiride and placebo, the patient will be analyzed in the glimepiride group.
- Randomized patients will be excluded from the safety population only if there is documented evidence (ie, all study dates recorded as no medication taken) that patients have not taken the study medication.

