1.3 DETERMINATION OF SAMPLE SIZE

The sample size/power calculations were performed based on the primary endpoint of change of HbA1c from Baseline to Week 52 in the intent-to-treat (ITT) population. Assuming a common standard deviation (SD) of 1.1%, and the true difference between sotagliflozin 400 mg and glimepiride is zero, 310 patients in the sotagliflozin 400 mg and glimepiride groups will ensure that the upper bound of the 2-sided 95% confidence interval (CI) of the adjusted mean difference is below 0.3% with at least 90% power. This sample size will have 80% power to test the non-inferiority of change of HbA1c from Baseline to Week 52 in completers, with a 30% dropout rate.

A sample size of 310 patients in sotagliflozin 400 mg group and 155 patients in placebo group will have more than 99% power to detect a treatment difference of 0.6% in mean HbA1c change from Baseline to Week 26 between sotagliflozin 400 mg and placebo (SD 1.2%; 2-sided 5% significance level).

A sample size of 155 patients in sotagliflozin 200 mg group and 155 patients in placebo group will have 95% power to detect a treatment difference of 0.5% in mean HbA1c change from Baseline to Week 26 between sotagliflozin 200 mg and placebo (SD 1.2%; 2-sided 5% significance level).

The total sample size is 930 patients to be randomized (sotagliflozin 400 mg group: 310; sotagliflozin 200 mg group: 155; glimepiride: 310; placebo: 155).

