2.4.3 Extent of investigational medicinal product exposure and compliance

The extent of IMP exposure and compliance will be assessed and summarized by actual treatment within the safety population ([Section 2.3.2](#)) unless otherwise specified.

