2.4.5.2 Analyses of adverse events

Generalities

The primary focus of adverse event reporting will be on TEAEs. Pretreatment and posttreatment AEs will be described separately.

If an adverse event date/time of onset (occurrence, worsening, or becoming serious) is incomplete, an imputation algorithm will be used to classify the adverse event as pretreatment, treatment-emergent, or posttreatment. The algorithm for imputing date/time of onset will be conservative and will classify an adverse event as treatment emergent unless there is definitive information to determine it is pretreatment or posttreatment. Details on classification of adverse events with missing or partial onset dates are provided in [Section 2.5.3](#).

Adverse event incidence tables will present by SOC, HLG, HLT, and PT, sorted by the internationally agreed order for SOCs and in alphabetic order for HLG, HLT and PT within a SOC for each treatment group, the number (n) and percentage (%) of patients experiencing an adverse event. Multiple occurrences of the same event in the same patient will be counted only once in the tables within a treatment phase. The denominator for computation of percentages is the safety population within each treatment group.

Sorting within tables ensures the same presentation for the set of all AEs within the observation period (pretreatment, treatment-emergent, and posttreatment). For that purpose, the table of all TEAEs presented by SOC and PT sorted by the internationally agreed SOC order and decreasing frequency of PTs within SOCs will define the presentation order for all other tables unless otherwise specified. In case of equal frequency regarding PTs, alphabetical order will be used.

Analysis of all treatment-emergent adverse events

The following TEAE summaries will be generated for the safety population.

- Overview of TEAEs, summarizing number (%) of patients with any
 - TEAE,
 - Serious TEAE,
 - TEAE leading to death,
 - TEAE leading to permanent treatment discontinuation.
- All TEAEs by primary SOC, showing number (%) of patients with at least one TEAE, sorted by internationally agreed order of primary SOC.
- All TEAEs by primary SOC, HLGT, HLT, and PT, showing number (%) of patients with at least one TEAE sorted by the SOC internationally agreed order. The other levels (HLGT, HLT, PT) will be presented in alphabetical order.

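### Patients who took both 400 mg and 200 mg kits are counted wholly in the 200 mg safety group, which flattens the dose comparison and can erase or reverse it for a rare event

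*SAP*

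**What the plan says.** The general principle in SAP 2.3.2 is as-treated: "Patients will be analyzed for safety analyses according to the treatment actually received". The section then sets rules for mixed exposure. The one at issue begins "For patients receiving both sotagliflozin 400 mg (treatment kits) and 200 mg (treatment kits) during the trial" and ends "the treatment group allocation for as-treated analysis will be sotagliflozin 200 mg group". Protocol 11.3.3 has the same rule: "the patient will be analyzed in the sotagliflozin 200 mg group". Neither document gives a threshold in kits or days, attributes events to the dose at onset, or states a reason.

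The other rules go the other way. Sotagliflozin with placebo, and sotagliflozin with glimepiride, both go to the sotagliflozin group. For the remaining pair: "For patients receiving both glimepiride and placebo during the trial, the treatment group allocation for as-treated analysis will be glimepiride group".

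The patient's data follow the allocation. For adverse events, SAP 2.4.5.2 states: "The denominator for computation of percentages is the safety population within each treatment group". For exposure, SAP 2.4.3 states: "The extent of IMP exposure and compliance will be assessed and summarized by actual treatment within the safety population". No safety table by randomized or predominant dose is specified.

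**The concern.** A 400 mg patient who takes one 200 mg kit by mistake becomes a 200 mg patient in every safety table. The events, the denominator and the exposure time all move. For someone treated mostly with 400 mg, that is not the treatment received.

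The direction matters too. In the other three rules the patient goes to the tested or active drug, which is the cautious choice for safety. Only the two-dose rule moves a patient to the lower exposure, away from the dose in the primary objective. At stake is the comparison of 400 mg with 200 mg, above all for rare events of special interest such as ketoacidosis, fracture or amputation, where one or two cases set the pattern.

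The trigger is foreseeable. The flow chart has eight double-blind dispensing visits, and SAP 2.2.1 lists erroneous kit dispensation among the irregularities to be identified prospectively.

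**Working it through.** **Inputs.** Group sizes are in SAP 1.3: "sotagliflozin 400 mg group: 310; sotagliflozin 200 mg group: 155; glimepiride: 310; placebo: 155". They reproduce from the 2:1:2:1 ratio: 930/6 = 155 per unit, giving 310, 155, 310 and 155. The number of mixed-kit patients (m) and the event rates are not in the documents, so they are assumed below and shown as ranges.

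**How little 200 mg is enough.** Double-blind kits are dispensed at Weeks 0, 2, 4, 8, 12, 18, 26 and 39, so the intervals are 2, 2, 4, 4, 6, 8, 13 and 13 weeks (total 52). If one wrong kit covers one interval, a completer spends at most 13/52 = 25% of treatment on the wrong dose and at least 75% on the assigned one. The rule still counts all 52 weeks as 200 mg.

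**Systematic effect.** Let m patients move from 400 mg to 200 mg, with the move unrelated to outcome and their risk that of the 400 mg group.

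- Expected 400 mg rate: (310 − m)·p400/(310 − m) = p400, unchanged.
- Expected 200 mg rate: (155·p200 + m·p400)/(155 + m).
- Expected difference: (p400 − p200)·155/(155 + m), a shrinkage of m/(155 + m).

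With assumed rates of 10% on 400 mg and 5% on 200 mg (true difference 5.00 points):

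| m | Shrinkage | 200 mg rate shown | Difference shown |
|---|---|---|---|
| 1 | 1/156 = 0.6% | 5.03% | 4.97 points |
| 5 | 5/160 = 3.1% | 5.16% | 4.84 points |
| 10 | 10/165 = 6.1% | 5.30% | 4.70 points |
| 31 (10% of the 400 mg arm) | 31/186 = 16.7% | 5.83% | 4.17 points |

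**One moved patient who carries the event (assumed counts).**

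| By randomized group (400 vs 200 mg) | Under the rule (400 vs 200 mg) |
|---|---|
| 31/310 vs 8/155 (10.00% vs 5.16%) | 30/309 vs 9/156 (9.71% vs 5.77%) |
| 3/310 vs 0/155 (0.97% vs 0%) | 2/309 vs 1/156 (0.65% vs 0.64%) |
| 2/310 vs 0/155 (0.65% vs 0%) | 1/309 vs 1/156 (0.32% vs 0.64%) |

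For the common event the picture barely changes. For the rare event the dose difference disappears in the second row and reverses in the third.

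**The opposite rule.** Sending all mixed-kit patients to 400 mg would dilute through 200 mg patients who took a 400 mg kit, by m/(310 + m): 0.3% for one, 3.1% for ten. Suppose 1% of each dose arm takes a kit of the other dose. The current rule then shrinks the difference by 3.1/158.1 = 2.0%, and the opposite rule by 1.55/311.55 = 0.5%. The 2:1 allocation makes the present direction the worse of the two.

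**The case against.** A reader might infer that the rule lowers 400 mg event rates and hides dose-related harm. The documents do not support that. The denominator moves with the patient, so the expected 400 mg rate, and its comparison with placebo and glimepiride, is unchanged. A mover without the event raises the 400 mg rate slightly: 31/310 = 10.00% becomes 31/309 = 10.03%. The 200 mg rate rises by about 0.6 points only when the moved patient has the event.

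A reader might also infer that the rule was chosen to favour the primary dose. No rationale is given either way, and the 200 mg dose has its own confirmatory hypotheses (SAP 2.4.4.4), so loading events onto it is no clear advantage. Nor do protocol and SAP conflict: they agree.

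The number moved may be very small. Kits are allocated centrally by IRT to match the assigned group (Protocol 8.4). A wrong kit need not be a 200 mg kit: it may contain the correct product (SAP 2.2.1), and a 400 mg patient given a placebo tablet kit stays with sotagliflozin.

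Such patients would also be visible. Those not treated as randomized are listed (SAP 2.2), irregularities are documented in the study report (SAP 2.2.1), and adjudicated events and amputations are listed individually (SAP 2.4.5.2).

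All of this stands as a limit on size. But listings do not correct the summary tables, and because the safety analysis is descriptive without planned testing (SAP 2.4.5), those tables carry the main safety message.

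**Conclusion.** The rule is inconsistent with the plan's own as-treated principle for a patient treated mainly with 400 mg, and it is the only mixed-exposure rule that moves a patient to the lower exposure. Its systematic effect is confined to the 200 mg rate and the 400-versus-200 contrast, which shrinks by 0.6% for one moved patient and 3.1% for five. For common events that is negligible unless many patients are moved. For a rare event in a moved patient, one case is enough to erase or reverse the dose order.

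This rests on three assumptions: moves unrelated to outcome, 400 mg risk in the moved patients, and illustrative counts and rates. The first is approximate, since patients who stay on treatment longer have more dispensing visits at which an error can occur. Whether any patient is affected cannot be told from the documents. The point deserves correction, but it does not undermine the safety analysis as a whole.

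**What to change.** In SAP 2.3.2 and Protocol 11.3.3, allocate patients who took both 400 mg and 200 mg kits to the dose taken for the longest time, with ties to 400 mg. A completer with a single dispensing error then stays in the group of the dose mainly taken. This is better than sending every such patient to 400 mg, which swaps one all-or-nothing rule for another, though one that dilutes less.

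SAP section 4 gives the database lock as 12 September 2019, and SAP version 3 is dated 3 April 2020, so changing the primary allocation now would be a post-lock change. If the prespecified rule is kept for that reason, state its rationale and report the number of mixed-kit patients, who should already be identifiable. If the number is not zero, add adverse event and EOSI tables by randomized or predominant dose. Keep the existing listings in either case.

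The cost is one line of text in each document or one supplementary set of tables. The remaining drawback is that a patient with mixed exposure is still counted under a single dose.

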2.4 STATISTICAL METHODS

2.4.1 Demographics and baseline characteristics

Continuous data will be summarized using the number of available data, mean, SD, median, minimum, and maximum for each treatment group. Categorical and ordinal data will be summarized using the number and percentage of patients in each treatment group.

Parameters will be summarized on the randomized population analyzed in the treatment group to which they were randomized. Analyses for the safety population will be included in the appendices if the size of the safety population is different (>10%) from the size of that in the primary analysis population (ie, randomized patients) for any treatment group.

Parameters described in [Section 2.1.1](#) will be summarized by treatment group and overall treatment groups using descriptive statistics.

P-values on demographic and baseline characteristic data will not be calculated.

No specific description of the safety parameters will be provided at baseline. If relevant, the baseline values will be described along with each safety analysis.

No specific description of the efficacy parameters will be provided at baseline. If relevant, the baseline values will be described along with each efficacy analysis.

2.4.2 Prior or concomitant medications

The prior, concomitant and posttreatment medications will be presented in the randomized population for each treatment group (and overall for the summary of prior medications), using counts and percentages of patients. Statistical tests for the between-group differences will not be performed.

Medications will be summarized by treatment group according to the WHO-DD dictionary, considering the first digit of the anatomical therapeutic chemical (ATC) class (anatomic category) and the first three digits of the ATC class (therapeutic category). A given medication may be linked to more than one ATC classes. All ATC codes corresponding to a medication will be summarized, and patients will be counted once in each ATC category (anatomic or therapeutic) linked to the medication. Therefore patients may be counted several times for the same medication.

Prior medications will be presented by anatomic and therapeutic categories and sorted by decreasing frequency of ATC based on the overall incidence across treatment groups. In case of equal frequency regarding ATCs (anatomic or therapeutic categories), alphabetical order will be used.

Concomitant and posttreatment medications will be presented by anatomic and therapeutic categories and sorted by decreasing frequency of ATC based on the incidence in the sotagliflozin 400 mg group. In case of equal frequency regarding ATCs (anatomic or therapeutic categories), alphabetical order will be used.

Antihypertensive medications will be presented separately by pharmacological class, chemical class and standardized medication name.

2.4.3 Extent of investigational medicinal product exposure and compliance

The extent of IMP exposure and compliance will be assessed and summarized by actual treatment within the safety population ([Section 2.3.2](#)) unless otherwise specified.

2.4.3.1 Extent of investigational medicinal product exposure

The extent of IMP exposure will be assessed by the duration of IMP exposure, and actual dose information.

Duration of IMP exposure is defined as last double-blind IMP dose date - first double-blind IMP dose date + 1 day, regardless of unplanned intermittent discontinuations (see [Section 2.5.3](#) for calculation in case of missing or incomplete data).

Duration of IMP exposure will be summarized descriptively as a quantitative variable (number of patients exposed, mean, SD, median, minimum, and maximum). In addition, duration of treatment exposure will also be summarized categorically by numbers and percentages for each of the following categories and cumulatively according to these categories:

- 1 to 28 days.
- 29 to 56 days.
- 57 to 84 days.
- 85 to 126 days.
- 127 to 182 days.
- 183 to 364 days.
- >364 days.

Additionally, the cumulative duration of treatment exposure will be provided, defined as the sum of the duration of treatment exposure for all patients, and will be expressed in patient years.

Number and percentage of patients by final dose at the end of the treatment will also be presented by each active treatment group.

Glimepiride (matching placebo) dose information will be assessed using ITT population by the following variables for each treatment group according to the treatment group to which they are randomized:

- The final dose at the end of the titration period, recorded at Visit 9 (Week 18).
- The final dose at the end of the treatment.
- Maximal tolerable dose: the MTD recorded at Visit 9 (Week 18) if MTD is checked in e-CRF.

Dose information variables will be summarized descriptively (number, mean, SD, median, minimum, and maximum).

Number and percentage of patients by final dose of glimepiride (matching placebo), MTD status and MTD at the end of the titration period (recorded at Visit 9), and by final dose of glimepiride (matching placebo) at the end of the treatment will also be presented by each treatment group.

